7.3 Committees

A steering committee and an executive committee were formed to set policy and govern the conduct of the study.

Steering Committee: Serves as the primary governing body of the study; responsible for policy decisions; provides oversight in planning the overall study design, facilitates the conduct and monitoring of the study, and reporting study results; votes on and approves all major decisions, final protocol and subsequent amendments. Members consist of principal investigators of the clinical centers, ancillary studies, the coordinating center, and the NIDDK project scientist. A chairperson and co-chair are appointed by the NIDDK from among the clinical center PIs.

Executive Committee: Manages day-to-day issues of the study; makes decisions required between the Steering Committee meetings, as needed for efficient progress of the study, and reports its actions to the Steering Committee on a regular basis; organizes and sets agendas for Steering Committee meetings. Members consist of the Steering Committee chair and co-chair, the Coordinating Center PI, NIDDK Project Scientist, and the DDDN Division Director.

7.4 Subcommittees

Subcommittees were formed to work on specific areas of the study and to make recommendations to the Steering Committee. Members consist of investigators from the clinical sites, ancillary studies, Coordinating Center, and NIDDK, including individuals with expertise in the relevant areas. The subcommittees and their missions are:

Adherence Subcommittee: Develop methods and questionnaires used to assess adherence and compliance in this study; define criteria for inclusion and exclusion based upon preliminary assessment of likelihood of compliance; develop plans to analyze and quantify compliance and its correlation with response. The final decision of which instruments and methods to use to measure adherence and compliance will be made by the Steering Committee upon the recommendations of the Adherence Committee.

Ancillary Subcommittee: Make recommendations on ancillary studies and prepare guidance for conduct of the ancillary studies and interactions and communications with the Clinical Centers and Data Coordinating Center; review proposals for ancillary studies and make detailed recommendations to the Steering Committee regarding which studies should be supported as well as how they impact on the overall clinical study; make recommendations to the Steering Committee and NIDDK regarding opportunities for other ancillary studies not initially planned in the grant applications that might be included in the Virahep C study; prepare detailed protocol for the timing, amounts, and characteristics of the clinical material to be gathered from patients for the ancillary studies. These protocols should be coordinated with the clinical protocol and must address issues of practicality and safety of the collection, with assurances that the ancillary studies do not interfere with clinical care of patients or responses. Prepare sections of the consent documents dealing with gathering of ancillary study materials, or prepare separate consent forms as necessary. Provide an

interface between the principal investigators on the ancillary studies and the Data Coordinating and Clinical Centers.

Coordinators Subcommittee: Attend to the day-to-day operations of the study including recruitment, protocol adherence, consistent and complete data collection at each clinical center. Make recommendations to the Steering Committee regarding any study issues that may require modification or resolution.

Exemption Subcommittee: Review on a case by case basis, protocol exemption petitions for subjects who do not meet one or more of the eligibility criteria (inclusion and exclusion).

Measurement Subcommittee: Develop parts of the protocol that require special forms and assessments that go beyond typical clinical assessment; develop means of assessing race and ethnic background of patients, with careful and detailed description of how the assessment will be performed and interpreted; develop or select other instruments to be used to assess and monitor patients, such as socioeconomic questionnaires, risk-factor questionnaires, depression and anxiety scales, symptom scales and quality of life questionnaires. The final decision on adoption of the specific measure instrument will be made by the Steering Committee after recommendations from the Measurements Subcommittee.

Pathology Subcommittee: Develop the policy for liver biopsies, the handling and mailing of samples to a central pathologist, the definition of an adequate sample (in ml and quality, numbers of stains or slides available, timeliness) and develop the scale and grading system to be used in the study; help in the analysis of data as relates to histological features. A central pathologist will read all slides but will be assisted by two or three pathologists from the individual clinical centers.

Protocol Subcommittee: Prepare the final written protocol for the study and thus prepare summary, background information, study design, inclusion and exclusion criteria, treatment regimen, monitoring schedule, adverse event grading and criteria for dose modification and drug discontinuation, statistical analysis, patient protection, and references sections of the protocol; develop details of the protocol and study design, but major decisions in the design and the final protocol will be approved by the Steering Committee. A subcommittee of the Protocol Committee will prepare the master consent form for the study.

Publications/Presentations Subcommittee: Develop the policy for publications in regards to preparation of manuscripts, assignment of tasks in analysis and writing, policy as regards to requesting data analysis, authorship policy and other issues related to publications. Prepare a formal publication policy for both full manuscripts and abstracts; prepare a list of possible publications that will arise from this study and prepare paragraphs regarding the scope of each and how they intersect with the probably final major manuscript to arise from this study.

Safety Subcommittee: Develop policy regarding reporting of adverse events; review all serious adverse events with appropriate timeliness; prepare annual reports as necessary.

Virology Subcommittee: Prepare the details of how viral kinetics will be assessed and what specialized virological testing will be performed, including timing of samples and assays to be done on all patients as well as a more carefully assessed subset of patients; prepare detailed document of how to perform the viral kinetic study, prepare and handle the blood samples and ship to the central virology laboratory; recommend the virological assays to be performed on specimens including conventional commercial assays such as quantitative and qualitative PCR for HCV RNA as well as special virological testing such as genotyping, quasispecies determination, and genome sequencing. Prepare the part of the protocol dealing with virological testing; provide oversight and monitoring of accuracy of the virology testing laboratory; aid in the analysis and interpretation of the virological testing results. The final decision on which virological assays will be used in the study will be made by the Steering Committee.

Website Subcommittee: Create and maintain a website for public consumption. The website will include general information about hepatitis C; a description of the Virahep-C study, including the goals of the study and its ancillary projects; and contact information at the clinical sites for persons interested in enrolling the study.

7.5 Data and Safety Monitoring Board

A Data and Safety Monitoring Board (DSMB) consisting of five individuals who are independent of the institutions and investigators participating in the clinical study, who have no financial ties to the outcome of the trial has been appointed by the NIDDK in consultation with the Steering Committee. Written documentation attesting to the absence of conflict of interest will be required of all DSMB members on an annual basis. The ongoing review of the data by this independent committee assures the investigators and the NIDDK that the trial can continue without jeopardizing patient safety. The roster and charter of the DSMB members will be given to each investigator participating in the study for submission to their IRB.

The DSMB is comprised of experts in the fields of hepatology, clinical trial methodology, biostatistics and ethics. The members are: [name] (Cedars-Sinai Medical Center), [name] (University of Texas Medical Branch, Galveston), [name] (University of Pennsylvania), [name] (Massachusetts General Hospital), and [name] (Virginia Commonwealth University). A DSMB chairperson ([name]) and a Medical Safety Officer ([name], Co-Investigator, Coordinating Center) have been appointed. The Medical Safety Officer will serve as the contact person for adverse event reporting. An NIDDK executive secretary ([name]) will be present for all DSMB meetings.

The DSMB will review the study protocol, recommend recruitment initiation, monitor all aspects of the study (e.g., recruitment, protocol deviations, adherence, adverse events, site visit summaries, data quality, attrition, descriptive characteristics, efficacy), and recommend protocol modifications, including early study termination.

Quarterly reports will be prepared by the Coordinating Center. Tables showing study progress will be presented by clinical center and overall. These will include recruitment, protocol deviations, adherence, attrition, adverse events, data quality, descriptive characteristics of the study sample, and efficacy.

All adverse events will be reported to the Medical Safety Officer, [name] for review. [name] will distribute reports of serious adverse events (SAE), which are both unexpected and related to the study medication, to the DSMB, the FDA, and all participating clinical centers so that they may submit the report to their local Institutional Review Board. Note that an adverse event is classified as serious if it results in one of the following: hospitalization or prolonged hospitalization; life-threatening; death; significant or permanent disability; congenital anomaly/birth defect (in the case of an unanticipated birth to a study participant); or requires intervention to prevent permanent damage.

The Coordinating Center will work with [name] and the Steering Committee to maintain a cumulative summary of adverse events overall and stratified by serious/non-serious status that will be forwarded to the DSMB every three months.

The DSMB will meet twice yearly, once in person and once via teleconference to review the cumulative data. A closed session will be held to review safety and data quality. Based on the data presented, the DSMB will recommend continuation or termination of the study. For example, the DSMB may recommend stopping the trial prematurely if the incidence of SAE is excessive. A summary of the DSMB findings will be forwarded to all investigators for submission to their respective IRBs.

8.0 Ancillary Studies

In order to reach specific aims 2 and 3 described in this protocol, a number of ancillary studies are planned utilizing the data and specimens derived from the treatment cohorts. These studies will include investigations of hepatitis C viral kinetics, immunology, genetic studies (patient and virus), and interferon signaling. These studies are described in detail below:

8.1 Viral Kinetics

The kinetics of HCV response to interferon have been recently described to undergo a biphasic response with the 1st phase being rapid, dose-dependent and accounting for a 0.5 to 2.0-log drop in HCV RNA levels

within 24 hours. This phase reflects the effectiveness of interferon in blocking viral production. A 2nd slower phase of viral decline follows which is not interferon dose dependent, reflects the death of HCV infected liver cells and correlates with the serum half-life of interferon. Its decline slope is an excellent predictor of SVR with interferon monotherapy or combination therapy. In preliminary results, it has been shown that SVR may be predicted as early as 24 hrs of initiating interferon based on 1st phase kinetic parameters. Therefore, the first specific aim of this study is to assess the best and earliest predictor(s) of SVR using viral kinetic modeling principles. In preliminary studies, it has been shown that African American patients treated with interferon alone have a blunted 1st phase viral decline but more importantly, a significantly slower 2nd phase viral decline. Based on preliminary findings that 2nd phase decline correlates directly with interferon half-life and that SVR may be improved in African American patients treated with peginterferon. Peginterferon in combination with ribavirin will likely optimize response.

Rationale for Viral Kinetics and Peginterferon alfa-2a Pharmacokinetics and Pharmacodynamics - Treatment Design

The purpose of this study is to:

- 1. Optimize treatment for patients who are infected with genotype 1 virus and are inherently more resistant to standard interferon treatment protocols.
- 2. Provide a clinical framework to understand why certain patients or races are inherently more resistant to interferon.
- 3. Understand the dynamics of HCV response in order to determine whether therapy can be discontinued earlier in patients who are resistant to current therapy and unlikely to respond. In order to assess the earliest time point(s) that can predict SVR we propose performing dynamic kinetic studies to assess viral kinetic parameters and their relationship to SVR. Serum sampling will occur at various time points (see Table 9 for measurement of HCV RNA, peginterferon alfa-2a levels, and 2',5'-OAS serum activity (a marker of interferon induction).

	Baseline (Day 0)			Da	у		Month						
		1	2	7	14	28	2 (Wk8)	3 (Wk12)	6 (Wk24)	12 (Wk48)	15 (Wk 60)	18 (Wk 72)	24 (Wk96)
Viral Kinetics	X	Х	Х	Х	Х	Х	Х	Х	Х	Х		Х	Х
Pharmaco -kinetics	X	X	x	X	Х	X	Х	Х	Х	Х	X PEG- IFN alfa-2a only		
ALT	Х	Х	Х	Х	Х	Х	Х	Х	Х	Х		Х	Х

 Table 9

 Blood sampling schedule for viral kinetic studies

Blood will be drawn for HCV RNA determination at baseline, days 1, 2, 7, 14, 28 and months 2, 3, 6, 12, 18 and 24 (see Table 9). The frequency of this sampling is to assess the early and late declines with peginterferon alfa-2a and whether there are differences in interferon effectiveness, intrinsic viral clearance, and viral production. Blood for peginterferon alfa-2a serum levels will be obtained at each point where we measure RNA in the first week and selected later time points (see Table 9). 2',5'-OAS, a marker of interferon responsiveness, will also be measured at these time points.

8.2 Ancillary Studies of Mechanisms of Antiviral Resistance

The following ancillary studies focus on determining the possible mechanisms underlying response/nonresponse to anti-viral therapy among African Americans, specifically, and among HCV-infected individuals, in general. Crucial to each of these studies is the availability of a large sample size of African Americans and Caucasian participants, detailed clinical information including, but not limited to, histological severity, viral load and HCV genotype and response to therapy, and access to optimally collected serum, PBMCs and liver tissue at specified timepoints. These four studies will evaluate virological factors, host genetics, interferon signaling pathways, and immunologic response in African American and Caucasian participants treated with peginterferon and ribavirin.

All of the ancillary studies will be collecting samples on all Virahep-C study participants (n=400) at baseline. Each of the ancillary studies, except for the Patient Genetics study, will continue to collect samples on all subjects up to and including the visit occurring at 4 weeks after the initiation of treatment. Beyond 4 weeks, specimens will be collected on all patients for Viral Genetics, Viral Kinetics, Pharmacokinetics and Immunology (CD4+) studies, and on a subset of patients for Interferon Signaling (at least n=72) and Immunology (CD8+, n=100) studies.

Consent for participation in the ancillary studies will be included in the main protocol consent with the exception of the larger volume blood draw needed at the end of follow-up (post treatment week 24) in 100 participants for the CD8+ Immunology study. A separate consent document will be created for this study. The ancillary studies require whole blood or plasma. Liver tissue will be used for pathology (minimum length of 1 cm if Trucut needle and 2 cm if Jamashedi or other skinny needle) and any additional tissue collected will be banked for future studies using a standardized method which is optimal for RNA preservation.

A summary of the specimens required and the timepoints for obtaining these specimens are summarized in Tables 13-14.

8.2.1 Viral Genetics Ancillary Study

Principal Investigator: [name] St. Louis University, St. Louis

Background and Rationale:

HCV replicates as a collection of quasispecies, and this underlies much of its biology, especially in immune evasion and in antiviral resistance. We will therefore study the impact of therapy for HCV on quasispecies development and on RNA replication in African Americans and Caucasians. We will sequence the complete viral genomes from a minimum of 96 patients undergoing therapy and then clone, express, and analyze the HCV RNA polymerase that replicates the viral genome from patients with representative RNA polymerase sequences. These studies will provide a comprehensive view of the HCV genome during therapy that may allow us to identify viral factors underlying the difference in response to antiviral therapy between African Americans and Caucasians. They will also provide data about RNA replication that may guide development of novel antiviral therapies.

Study Aim:

To characterize HCV genetic heterogeneity by sequence and quasispecies in patients with flat, slow, and rapid early responses to antiviral therapy. The functional consequences of variation in the NS5B RdRp gene will be determined.

Study Endpoints:

- (a) Quasispecies distribution and complexity in African Americans and Caucasians.
- (b) Quasispecies distribution and complexity as a predictor of non-response, early and late response.
- (c) Specific HCV sequences (within entire genome) predictive of non-response, early and late response.
- (d) Correlate HCV RdRp activity with genetic drift and clinical response.

Study Population:

Minimum of n=96 with 6 groups of no less than 16 each (Groups: flat, rapid and slow responders for both African American and Caucasian groups). Note that serum will be obtained from all 400 patients for four

weeks for two reasons. First, to be able to increase the statistical power of the Viral Genetics study by sequencing short regions of genomes derived from additional patients. Second, to be able to expand the specific regions of the genome sequenced to identify individual viral variations that may affect or aid in the interpretation of the results of the other ancillary studies (e.g., sequence the NS3 region of all immunology patients so that the epitopes present in each patient are known).

Method for Analysis/Power Calculations:

Note: The power calculations are based on 96 patients, or the smallest sample size that would be used for this study.

Comparing HCV genetic sequences within race groups:

A test for proportions will be used to compare the proportion of Caucasians to that of African Americans who have (or don't have) a particular HCV genetic sequence. Given a sample size of 96 subjects with equal numbers of Caucasians and African Americans (48 in each group), and using a two-tailed test with α = 0.05, we will have 80% power to detect that 35% of one race have the particular sequence versus 10% in the other racial group. This corresponds to an odds ratio of approximately 4.8.

Comparing HCV genetic sequences within responder groups:

Data will be analyzed using a chi-square test to compare the proportions among the three responder groups (defined above) that have (or don't have) a particular genetic sequence.

Given a sample size of 96 subjects, divided into 3 evenly-sized responder groups, there will be 80% power to detect an effect size of 0.32 at α = 0.05 using a two-sided test. An effect size for a chi-square test of 0.32 is considered to be small to medium.²⁹ An example of proportions across 3 groups yielding an effect size of approximately 0.32 is 10%, 27%, 44% (or conversely, 90%, 73%, 56%).

HCV RdRp

Logistic regression models will be fit to: (1) analyze the association between RdRp activity and particular sequence patterns in the viral genomic sequence; and (2) analyze the association between RdRp activity and response (e.g., null responder vs. responder). RdRp can be classified as both a categorical variable (e.g., activity greater than twice the normal levels) and continuous variable (i.e., the percentage of activity that is consistent with a standard RdRp).

RdRp activity will be analyzed as a categorical and continuous predictor variable with response as the outcome variable. Given that by study design one-third (n=32) of the patients will be null responders, there will be 80% power to detect an odds ratio of 3.8 for being a null responder if the RdRp activity is greater than twice the normal level at α = 0.05 and using a two-tailed test. Keeping RdRp continuous (and performing transformations to ensure normality), we will have 80% power to detect an odds ratio of 2.2 for a standard deviation increase from the mean of the transformed RdRp level using a two-sided test with an alpha of 0.05.

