An important recent finding is that there are considerable racial differences in epidemiology, typical course, natural history and response to treatment of hepatitis C.¹³ The same population based surveys mentioned above demonstrated that African Americans have a higher rate of anti-HCV than Caucasians (3.2% vs. 1.8%) and a higher proportion have detectable HCV RNA (86% vs. 68%).^{1,13} These findings suggest that HCV infection is more common among African Americans than whites and that once infected, African Americans are also more likely to develop chronic infection. Findings from other cohort studies support these findings, but the reasons for these differences remain unknown.

The hepatitis C virus exists as at least six genotypes and several subtypes (1a, 1b, 2a, 2b, etc). Genotype 1 accounts for approximately 75% of HCV infections in the United States, genotype 2 for 10-15%, genotype 3 for 5-10%, and other genotypes and mixed infections for the remainder. The distribution of different genotypes in the United States also varies by race. Thus, genotype 1 affects 91% of African Americans compared to only 67% of whites. Genotype 1b is particularly more common among blacks (36%) than whites (18%) while genotype 3a is rare (<1% vs. 6%).¹³ Again the reasons for these differences are not clear. Furthermore, other racial groups, such as Hispanic whites and Asians in the United States, more closely resemble whites than African Americans in rates of chronicity and in genotype distribution.

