The proportion of African Americans and Caucasians with SVR will be compared using the chi-square test of association. The association between race and SVR after adjusting for potential confounders such as adherence, HCV sub-genotype, initial viral level, ALT, body mass index, and baseline histology will be assessed through multiple logistic regression analyses. The Hosmer-Lemeshow statistic will be calculated to determine if there is evidence that the final multiple logistic regression model does not fit. ²³ These

analyses will be repeated for durable viral response, i.e., having undetectable viral RNA 12 months following treatment discontinuation.

Generalized estimating equation (GEE) methods of Zeger and Liang.^{24,25} will be used to assess the differences between the racial groups with respect to changes in serum HCV RNA levels during therapy. This approach models both the regression of the response variable on the independent variables and accounts for the correlated nature of the responses. Analyses using conventional regression methods could provide erroneous variance estimates and loss of statistical efficiency because of the conventional assumption that each response is statistically independent. As a result, invalid inferences could be made if the conventional approach were applied to these longitudinal data.

The models examining response to treatment will include measures of adherence. As an initial step in examining adherence, graphical displays of the dosing history of each participant will be plotted and compared to the prescribed dosing regimen. Graphs include chronological plots showing the date and time of dose intake and frequency histograms of inter-dose intervals. The inter-dose interval representing the length of time between two successive doses will be calculated. For ribavirin, the optimal inter-dose interval is 12 hours and for peginterferon it is 7 days. Longer dosing intervals represent non-adherence and times in which the participant theoretically did not have adequate inhibitory drug concentration. In addition, summary statistics of adherence such as the percentage of prescribed doses taken and the percentage of drug holidays will be derived from the MEMS cap data. GEEs with multiple responses and adherence as a time-dependent covariate will be examined.

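### The between-race test of HCV sequences in Section 8.2.1 is not stratified by subtype, so a subtype-linked position can reach significance with no race difference within subtype

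*Protocol*

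**What the plan says.** Section 8.2.1 of the Protocol fixes the method for the race comparison: "A test for proportions will be used to compare the proportion of Caucasians to that of African Americans" who carry, or do not carry, a particular sequence. The minimum sample is 96, or 48 per race, made up of six race-by-early-response groups of at least 16. On power it states: "we will have 80% power to detect that 35% of one race have the particular sequence versus 10% in the other racial group". It adds: "This corresponds to an odds ratio of approximately 4.8". Serum is kept from all 400 participants so that short regions can be sequenced in further patients; how many is not stated.

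Section 8.2.1 does not stratify, restrict or adjust this comparison by subtype. Section 3.3 admits genotype 1 without limiting subtype.

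Other parts of the Protocol bear on the point:

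- Section 1.1 gives genotype 1 in 91% of African Americans and 67% of whites, and genotype 1b in 36% and 18%.
- Section 6.0 plans the race-SVR model "adjusting for potential confounders such as adherence, HCV sub-genotype, initial viral level" and other baseline variables.
- Section 8.2.2 (Patient Genetics) provides for Mantel-Haenszel or logistic control if confounding appears.
- Section 8.2.4 limits the CD8 study to genotype 1a, without giving subtype confounding as the reason.

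**The concern.** The study looks for viral factors behind the racial difference in response. Subtypes 1a and 1b differ in sequence, and the Protocol's own background figures imply that the two races carry them in different proportions. At any position that tracks subtype, a crude comparison between races partly measures the subtype mix. A significant result there cannot be told apart from a variant that differs between races within the same subtype.

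Complete genomes are to be sequenced, so many positions are exposed. Positions tied to subtype also move together: if the sampled subtype imbalance happens to be large, many are flagged at once, and this could look like corroboration.

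**Working it through.** **1. The plan's own figure.** Inputs from Section 8.2.1: 48 per race, 35% v 10%, two-sided α = 0.05.

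- Odds ratio: (0.35/0.65)/(0.10/0.90) = 4.85, which agrees with the stated 4.8.
- Power by exact enumeration of two binomials: 79.8% with Fisher's exact test and 86.2% with the uncorrected test for proportions.

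The stated 80% is reproduced by Fisher's test and is not in dispute. Because the Protocol does not name the version of the test, both are carried forward.

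**2. Subtype mix within genotype 1.** The 36% and 18% in Section 1.1 are shares of all infections, so they must be divided by the genotype 1 shares:

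- African Americans: 0.36/0.91 = 39.6% 1b
- Whites: 0.18/0.67 = 26.9% 1b

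The gap is 12.7 points, not the raw 18. Section 1.1 gives no 1a figure; all other genotype 1 is taken as 1a.

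**3. Frequency of a subtype-linked sequence with no race effect.** Let q1 be the sequence frequency in 1b and q0 that in 1a, the same in both races. Then

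P(sequence | race) = s·q1 + (1 − s)·q0, where s is the 1b share in that race.

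The linkage values are assumptions, shown as a range:

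- Full linkage (q1 = 1, q0 = 0): 39.6% v 26.9%
- 90/10: 0.396×0.9 + 0.604×0.1 = 41.6%, against 0.269×0.9 + 0.731×0.1 = 31.5%
- 80/20: 0.396×0.8 + 0.604×0.2 = 43.7%, against 0.269×0.8 + 0.731×0.2 = 36.1%

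**4. Chance that the crude test gives p < 0.05 at 48 per race** (exact enumeration):

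| Linkage | Fisher | Uncorrected |
|---|---|---|
| Full | 19.3% | 26.5% |
| 90/10 | 12.3% | 17.7% |
| 80/20 | 7.9% | 11.7% |

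The nominal rate is 5%.

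**5. Sensitivity.**

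- *More patients.* If all 400 were sequenced (200 per race), the uncorrected rates would be 77% for full linkage, 56% for 90/10 and 34% for 80/20. The Protocol allows for this size but does not fix it.
- *Smaller subtype gap.* With an assumed 1b share of 35% v 30%, full linkage gives 8.4% at 48 per race and 18.7% at 200 per race (uncorrected).

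**6. Effect of stratifying** (simulation, 100,000 replicates, Section 1.1 mix). A Mantel-Haenszel test by subtype rejects in 4.8% (90/10) and 4.9% (80/20) of samples at 48 per race, and in about 5% at 200 per race. For a true 35% v 10% race difference unrelated to subtype, power at 48 per race is 85.1% stratified and 86.3% crude.

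**The case against.** **A subtype-linked difference is real.** The two groups' viruses do differ at that position, and if subtype contributes to the response gap it is one of the viral factors sought. This stands. The crude comparison answers a legitimate marginal question and should not be demoted to description. The problem is only in reading it as a race difference beyond subtype.

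**The inputs are uncertain.** Section 1.1 reports background data, while the trial takes US-born genotype 1 patients and selects the sequencing subset by early response. This stands too. The rates depend on the enrolled mix, and a smaller gap shrinks them.

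**An analysis plan could add the adjustment.** One may exist and is not shown. However, the Protocol does not leave the method open: it names a crude test here while providing for sub-genotype or confounding in Sections 6.0 and 8.2.2.

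**Stronger readings.** A reader might infer three things that the Protocol does not support:

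- *That every subtype-linked position will be reported as racial.* At 48 per race even a fully linked position is flagged in only about one sample in four or five.
- *That 77% describes the planned study.* It needs all 400 patients sequenced, and the only fixed size is the minimum of 96.
- *That the responder-group chi-square and the RdRp models share the defect.* With equal cells, race is balanced across response groups, so the racial subtype imbalance does not by itself carry over. The Protocol gives no figure linking 1a or 1b to response, and the RdRp logistic models have no covariate list that would exclude subtype.

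**Conclusion.** The point holds for the between-race sequence comparison in Section 8.2.1 and only there. As stated, that test can give a significant race difference at a subtype-linked position with no race difference within subtype. At the planned minimum of 48 per race the rate is about 19% to 27% for full linkage, 12% to 18% for 90/10 and 8% to 12% for 80/20, against a nominal 5%. The lower figure of each pair is Fisher's test and the upper the uncorrected test.

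These rates assume that the Section 1.1 subtype mix applies to the sequenced patients, that genotype 1 other than 1b is 1a, and that the linkage values are as illustrated. The primary endpoint and the stated 80% power are unaffected. This is a worthwhile, inexpensive improvement to an ancillary analysis.

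**What to change.** In Section 8.2.1, add to the between-race sequence comparison an analysis stratified by subtype 1a/1b, using either a Mantel-Haenszel test or logistic regression with race and a subtype term. Report it beside the crude comparison. State that any claim of a race-linked variant beyond subtype rests on the stratified result.

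The cost is a few lines of text, some extra analysis and about one point of power (86.3% − 85.1% = 1.2 points in the case checked). Sub-genotype is already needed for the Section 6.0 model, so no further sample, visit or patient is required.
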